Primary endpoint	Comparison of the two treatment modalities to reduce bioburden as determined by quantitative polymerase chain reaction (PCR) analysis, DNA sequencing.
Secondary endpoint	Comparison of the procedural pain from the two treatment modalities as determined by subject reported visual analog scale (VAS) pain scores. Comparison of the procedural bleeding from the two treatment modalities as determined by physician assessment. Procedural bleeding
Other evaluations	Overall subject satisfaction from the two treatment modalities.
Safety evaluations	Incidence of adverse events.
Planned interim analysis	Serious adverse events will be audited by the study team on an ongoing basis throughout the study duration.
Primary statistical analysis plan	Treatment effectiveness will be assessed by a two-sample t-test comparing the evaluation criterion at the two study intervals.
Rationale for number of subjects	This is a pilot study to determine treatment feasibility and efficacy.

SUBJECT INCLUSION CRITERIA

A subject will be eligible for inclusion in this study if ALL of the following criteria apply:

[figure not shown]
- Aged eighteen years or older
- Having an ulcer of any etiology
- Has signed the informed consent form prior to any study protocol related procedure
- Willing and able to adhere to protocol requirements

SUBJECT EXCLUSION CRITERIA

The subject will not be eligible for study inclusion if ANY of the following criteria apply:

- Any unstable medical condition that would cause the study treatment to be detrimental to the subject, as judged by the Principle Investigator
- Documented medical history of significant cardiac, pulmonary, gastrointestinal, endocrine (*other than Diabetes Mellitus type 1 or 2*), metabolic, neurological, hepatic or nephrologic disease would impede the subject's participation, as judged by the Principle Investigator
- Documented medical history of immunosuppression, immune deficiency disorder, or currently using immunosuppressive medications
- Having clinical presentation of active osteomyelitis
- Pregnancy or lactation
- Participation in another clinical study involving ulcers within thirty days prior to enrollment

STUDY DESIGN

ULCER DEBRIDEMENT

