3. Perform debridement procedure
 - Record technique or laser settings used during treatment
4. After debridement procedure:
 - Collect ulcer photos
 - Record VAS pain score, Present Pain Intensity, and Brief Pain Inventory
 - Record bleeding assessment
 - Collect biopsies
 - Provide Standard of Care

Follow Up Visit (Study Week Two):

- Subjects cross over to other study group
 - Remove ulcer dressing
1. Before debridement procedure:
 - Record VAS pain score, Present Pain Intensity, and Brief Pain Inventory
 - Collect ulcer photos and measurements
 - Collect biopsies
 2. Apply anesthetic
 3. Perform debridement procedure
 - Record technique or laser settings used during treatment
 4. After debridement procedure:
 - Collect ulcer photos
 - Record VAS pain score, Present Pain Intensity, and Brief Pain Inventory
 - Record bleeding assessment
 - Collect biopsies
 - Provide Standard of Care

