Efficacy of Laser Debridement on Pain and Bacterial Load in Chronic Wounds (NCT03182582)

Statistical Analysis Plan

February 6, 2018

[name], Principal Investigator
Stanford University
Stanford, California 94305

Methods:

This is a prospective, randomized, controlled, crossover clinical trial, entailing two groups: 1) one group receiving a single laser debridement session first, followed by a single sharp debridement session one week later; 2) the other group receiving a single sharp debridement session first, followed by a single laser debridement session one week later. Analysis variables include pain during debridement, pre- and post-debridement wound sizes, pre- and post-debridement bacterial loads, and patient preference.

Statistical Analysis:

The a priori power analysis presumes a 50% reduction in patient-reported pain. A sample size of 22 patients would be required to achieve 80% power, using a two-tailed test with $\alpha = 0.05$. Descriptive analyses include means (standard deviation). A paired t-test was planned to evaluate continuous data, and the 3x2 Fisher's exact test was planned to analyze categorical data. For all data analyses performed in the study, $p < 0.05$ is considered statistically significant.

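### The SAP's only rule for categorical data, a 3x2 Fisher's exact test, leaves the table undefined, and the ordinary tables would not give a sound laser-versus-sharp comparison in this crossover

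*SAP*

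**What the plan says.** The SAP (Methods) describes a randomized crossover "entailing two groups: 1) one group receiving a single laser debridement session first" and sharp debridement a week later, with the other group in the reverse order. Each patient therefore contributes a result under both treatments. The listed analysis variables end with "pre- and post-debridement bacterial loads, and patient preference". Preference is the only one of them that is clearly categorical, and its response options are not given.

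Under Statistical Analysis, "A paired t-test was planned to evaluate continuous data", and "the 3x2 Fisher's exact test was planned to analyze categorical data". Nothing further is said about categorical data: not the variable, the three levels, the two columns, or whether a patient is counted once or twice.

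The protocol does not fill the gap. The only test in its synopsis is for treatment effectiveness: "Treatment effectiveness will be assessed by a two-sample t-test comparing the evaluation criterion at the two study intervals". It adds two items that may be categorical. One is a secondary endpoint, "Comparison of the procedural bleeding from the two treatment modalities as determined by physician assessment"; the other, under other evaluations, is "Overall subject satisfaction from the two treatment modalities". The Study Schedule lists "Record bleeding assessment" after each of the two debridements, without a scale.

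**The concern.** A 3x2 table can be built from crossover data in several ways, and they answer different questions. Three natural ones are:

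- **A. Preference (laser/none/sharp) by sequence group.** This asks whether preference differs between the two orders of treatment. It does not ask whether patients prefer laser to sharp.
- **B. Three-level outcome by treatment.** This asks the right question, but it enters each patient twice as if the two results were independent.
- **C. Session preferred (first/none/second) by sequence group.** Here a preference for laser shows as first session in one group and second session in the other, so the test compares laser with sharp with one record per patient. The same table works for the better session on an outcome recorded twice.

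The list is not exhaustive. The SAP's sentence fits all three, so the conclusion on preference, and on bleeding or satisfaction if they are graded, can depend on a table that was not fixed in advance.

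**Working it through.** **Inputs.** From the SAP: 22 patients, two-sided 5% level, two sequences. From the protocol: twenty subjects, used as a second case. Assumed, because the documents give no values: response levels laser/none/sharp, true preference rates, sequence splits, and three grades for an outcome recorded twice. The plan attaches no figure to the Fisher test, so there is none to reproduce.

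**Formulas.** For a 3x2 table with row totals r1, r2, r3, first-column counts a1, a2, a3 with sum n1, and N patients in all, P = C(r1,a1)·C(r2,a2)·C(r3,a3) / C(N,n1). The p-value sums P over all tables no more probable than the one observed. The exact sign test is two-sided binomial with probability 1/2 among patients who state a preference. Rejection rates for preference are exact, by enumerating both sequences.

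**Step 1: all 22 prefer laser, 11 per sequence.**
- Table A: (11,0,0) v (11,0,0). Only one table has these margins, so p = 1.0.
- Table C: (11,0,0) v (0,0,11). p = 2/C(22,11) = 2/705,432, below 0.0001.
- Sign test: 2 × (1/2)^22, below 0.0001.

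**Step 2: a less extreme result, 15 laser, 4 none, 3 sharp.**
- Table A: (8,2,1) v (7,2,2), p = 1.0.
- Table C: (8,2,1) v (2,2,7), p = 0.014.
- Sign test, 15 of 18: 2 × (816+153+18+1)/262,144 = 2 × 988/262,144 = 0.0075. The proportion is 83%, 95% CI 59 to 96%.

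**Step 3: rejection rates with equal sequences.**

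| Assumed truth | n | Table A | Table C | Sign test |
|---|---|---|---|---|
| 60/20/20 laser/none/sharp | 22 | 3.9% | 45% | 50% |
| 70/15/15 | 22 | 3.3% | 76% | 81% |
| 80/10/10 | 22 | 1.8% | 96% | 97% |
| 70/15/15 | 20 | 2.8% | 71% | 76% |
| Order effect only: 70% second session, 15% none, 15% first | 22 | 76% | 3.3% | 0.8% |

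Table A has almost no chance of detecting a treatment preference, and it rejects often when only the order matters.

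**Step 4: the same order effect with unequal sequences, n=22.** At 8+14, Table C rejects in 3.5% and the sign test in 4.0%. At 7+15 the figures are 3.3% and 7.7%. The sign test can therefore exceed 5% when the sequences are clearly unequal; Table C does not in these cases.

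**Step 5: Table B, an outcome recorded at both sessions.** Take grade totals of 10/8/4 with laser and 4/10/8 with sharp. Fisher's test of (10,8,4) v (4,10,8) gives p = 0.16, however the patients pair up. One pairing with these totals has rows (sharp grade) by columns (laser grade) of [4,0,0; 6,4,0; 0,4,4]. That is 6+4 = 10 patients better with laser, 4+4+4 = 12 equal and none worse. The sign test gives 2 × (1/2)^10 = 0.002, and the session-by-sequence table (5,6,0) v (0,6,5) gives p = 0.005. The consistent within-patient difference is lost in Table B.

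In 10,000 simulated trials per setting (n=22, three grades equally likely under the null, bivariate normal latent score), Table B rejected under no treatment difference in 4.5%, 3.1%, 2.1% and 1.4% at within-patient correlation 0, 0.3, 0.5 and 0.7. It becomes conservative as the correlation rises. This illustrates direction only; it is not a power statement for bleeding, which has no stated scale.

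**The case against.** The strongest reply is that Table C is a legitimate crossover analysis and is itself a 3x2 Fisher's exact test. The SAP may have meant exactly that, in which case nothing is wrong with the method. This stands. A reader might infer that Fisher's test is wrong for a crossover, or that the authors overlooked pairing because they name a paired test for continuous data only. The documents support neither inference. They show only that the table was not stated.

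A reader might also infer that counting patients twice produces false positives. With positive within-patient correlation the error runs the other way: Table B rejects too rarely.

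The reach is narrow. Preference is the only clearly categorical variable in the SAP. Satisfaction sits among the protocol's other evaluations. Bleeding is a secondary endpoint in the protocol, but it has no scale and is not in the SAP's list of variables. The protocol calls the trial a pilot. Every preference rate, grade and split used above is assumed. All of this stands, and it limits the weight of the point. It does not remove it: the SAP's sentence is the whole plan for preference, and the tables it permits can give p = 1.0 or p below 0.0001 on the same data.

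**Conclusion.** The point holds as a gap in specification. The SAP's one categorical rule permits a table that does not compare laser with sharp (A), a table that ignores the pairing (B) and a table that is valid (C), and it does not say which is meant. Of these three, only C is a sound laser-versus-sharp test.

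The size for preference at n=22, under an assumed 70/15/15 split and equal sequences, is 3.3% rejection for A against 76% for C and 81% for the sign test. Under the assumed pure order effect, A rejects in 76%. These figures rest on assumed response levels, preference rates and sequence splits; the p = 1.0 for unanimous preference needs only that preference is tabulated by sequence.

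A reader might extend the point to the trial's main results. The documents do not support that: the primary bioburden comparison and pain do not depend on this test. It is a minor point.

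**What to change.** In the SAP, name each categorical variable, its levels, the table and the unit of count.

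- **Patient preference.** Specify an exact sign (binomial) test of laser versus sharp among patients who state a preference, with the proportion and 95% CI, and report the number with no preference. The drawback is the one in Step 4: with an order effect and clearly unequal sequences it can exceed 5%. So state that the session-by-sequence Fisher table (first/none/second session preferred, by sequence) replaces it if the sequences are not balanced. Define the imbalance limit in advance and apply it to the sequence counts alone, without sight of the preference data. The Fisher table costs a little power when the sequences are equal (76% against 81% at 70/15/15, n=22).
- **Any categorical outcome recorded at both sessions (bleeding, if graded).** State the scale and name one within-patient test, such as the exact sign test. Choose a single test, because different paired tests can also disagree. Do not use Fisher's test of outcome by treatment.

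The cost is a few sentences in the SAP. The data collected and the number of patients do not change.
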